# **6.5.1** Recommended Hepatic Adverse Event Management Algorithm

Consider imaging for obstruction.

Toxicity		
(CTCAE v.4.03)	Management	Follow-up
Grade 1  AST or ALT > ULN to 3.0x ULN and/ or T. bilirubin > ULN to 1.5x ULN.	Continue protocol therapy	
 
Continue routine LFT monitoring according to the required clinical, laboratory evaluations in Section 8.2.
 
If worsens:
 
Treat as Grade 2 or 3-4.
 

Grade 2  AST or ALT > 3.0 to $\leq 5x$ ULN and/ or T. bilirubin > 1.5 to $\leq 3x$ ULN.	
 
Delay nivolumab per protocol
 
Increase LFT monitoring to every 3 days
 
	
 
If returns to baseline:
 
Continue routine LFT monitoring per the required clinical, laboratory evaluations in Section 8.2.
 
Resume protocol therapy
 

Grade 3 or 4  AST or ALT > 5 x  ULN or T. bili. > 3 x  ULN.	
 
Discontinue protocol therapy*
 
Increase LFT monitoring to every 1-2 days
 
	
 
If elevations persist >5-7 days or worsen:         
 
0.5-1mg/kg/day methylprednisolone IV or oral equivalent
 
When LFT returns to Grade 1 or baseline, taper steroids over at least 1 month
 
Upon improvement, nivolumab may be resumed after corticosteroid taper, if needed.
 
Consider prophylactic antibiotics for opportunistic infections
 
If worsening or no improvement occurs despite initiation of corticosteroids, corticosteroid dose should be increased to 1 to 2 mg/kg/day methylprednisolone equivalents and nivolumab must be permanently discontinued.
 
 
 
If improves to Grade 2:         
 
Taper steroids over at least 1 month.
 
 
 
If does not improve in > 3-5
 

		-

Patients on IV steroids may be switched to an equivalent dose of oral corticosteroids (e.g. prednisone) at start of tapering or earlier, once sustained clinical improvement is observed. Lower bioavailability of oral corticosteroids should be considered when switching to the equivalent dose of oral corticosteroids.

\*Nivolumab therapy may be delayed rather than discontinued if  $AST/ALT \le 8 \times ULN$  or T. bilirubin  $\le 5 \times ULN$ .

\*\* The recommended starting dose for Grade 4 hepatitis is 2 mg/kg/day methylprednisolone IV.

## **6.6** Dose Modifications for Gastrointestinal Adverse Events

Diarrhoea/	Management/Next Dose of Nivolumab	
Colitis		
Grade 1	Continue protocol therapy and treat symptomatically.	
Grade 2	• May observe and treat symptomatically for seven (7) days. If persists greater than seven (7) days, then off protocol therapy.	
Grade 3	Off protocol therapy.	
Grade 4	Off protocol therapy.	

Patients who require steroids should be taken off study treatment.

Evaluation for all patients for additional causes includes C. diff., acute, self-limited infectious, foodborne illness, ischemic bowel, diverticulitis, and IBD.

**Recommended management:** See GI AE management Algorithm below (see *Section 6.6.1*).

Other GI	Management/Next Dose of Nivolumab
Nausea/ Vomiting	
Grade 1	No change in dose.
Grade 2	
 
Hold pending evaluation for gastritis duodenitis and other immune adverse events or other causes. Resume at same dose level if resolution to ≤ Grade 1 within seven (7) days.
 

Grade 3	
 
Hold pending evaluation until ≤ Grade 1. Resume at same dose level. If symptoms do not resolve within seven (7) days with symptomatic treatment patients should go off protocol therapy
 

Grade 4	Off protocol therapy  Off protocol therapy  Office of the state o

Patients with grade 2 or 3 N-V should be evaluated for upper GI inflammation and other immune related events. Recommended Gastrointestinal Adverse Event Management Algorithm

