## 6.2 Dose Modifications for Non-Haematological Toxicity

Patients who have any Grade 3 or Grade 4 non-hematological toxicity attributable to the investigational drug with the specific exclusion of the following, will be removed from the study:

- Grade 3 ALT that returns to levels that meet initial eligibility criteria or baseline within seven (7) days and does not require systemic immunosuppression;
- Grade 3 liver enzyme elevation, including AST/GGT that returns to baseline within 7 days and does not require systemic immunosuppression;
- Grade 3 or 4 serum electrolyte or mineral abnormalities responsive to supplementation;
- Grade 3 or 4 amylase or lipase abnormalities that are not associated with diabetes mellitus (DM), associated liver or gall bladder inflammation or clinical manifestations of pancreatitis;
- isolated Grade 4 amylase or lipase abnormalities that are not associated with symptoms or clinical manifestations of pancreatitis and decrease to < Grade 4 within 1 week of onset;
- Grade 3 rash/oral lesions that resolves to Grade  $\leq 1$  within seven (7) days;
- Grade 3 or 4 seizures (multiple seizures despite medical intervention or life-threatening seizures/status epilepticus) that may occur in the context of pseudo-progression;
- fever greater than 40°C of ≤24 hr. duration;
- Grade 3 fatigue that resolves to Grade  $\leq 2$  within 7 days;
- Grade 3 creatinine increase that resolves to Grade  $\leq 1$  or baseline within seven (7) days.

Patients who experience the following non-hematological toxicities attributable to protocol therapy will also be removed from the study:

- Grade 2 fever that does not resolve to Grade  $\leq 1$  within seven (7) days;
- Grade 2 uveitis, eye pain or blurred vision that does not respond to topical therapy and does not improve to Grade 1 prior to next scheduled dose;
- Grade 2 non-hematological toxicity requiring systemic immunosuppressive therapy. This includes, but is not limited to, autoimmunity of the lung, heart, kidney, bowel, CNS, pituitary or eye;
- Grade 2 endocrine toxicity requiring hormone replacement, with the exception of Grade
   2 hypothyroidism, thyroiditis and thyroid dysfunction adequately managed with thyroid hormone replacement;
- Grade 2 adrenal insufficiency;
- Grade 3 colitis or Grade 3 diarrhea attributable to protocol therapy of more the seven (7) days of duration.

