# **6.6.1** Recommended GI Adverse Event Management Algorithm

Opiates/narcotics may mask symptoms of perforation. Infliximab should not be used in cases of perforation or sepsis.

Toxicity (CTCAE	Management	Follow-up
v.4.03)  Grade 1  Diarrhea: < 4 stools/ day over baseline.  Colitis: asymptomatic.	

Continue protocol therapy

Symptomatic treatment

	
 
Close monitoring for worsening symptoms.
 
Educate patient to report worsening immediately.
 
If worsens:
 
Treat as Grade 2 or 3/4
 

Grade 2 Diarrhea: 4-6 stools/ day over baseline; IV fluids indicated <24hrs; not interfering with ADL. Colitis: abdominal pain; blood in stool.	
 
Nivolumab should be withheld per protocol.
 
Symptomatic treatment
 
	
 
Resume protocol therapy
 
If persists > 5-7 days or recurs:
 
0.5-1.0mg/kg/day         methylprednisolone or oral         equivalent
 
When symptoms improve to         grade 1, taper steroids over at         least 1 month
 
Consider prophylactic         antibiotics for opportunistic         infections
 
Resume nivolumab per         protocol.
 
If worsens or persists > 3-5 days         with oral steroids:         
 
Treat as Grade 3 or 4 and

Grade 3 Diarrhea: ≥ 7 stools/ day over baseline; incontinence; IV fluid ≥ 24 hours; interfering with ADL Colitis: severe abdominal pain, medical intervention indicated, peritoneal signs	
 
Hold protocol therapy
 
Corticosteroids at dose of 1-2 mg/kg/day methylprednisolone IV or IV equivalent
 
Add prophylactic antibiotics for opportunistic infections
 
Consider lower endoscopy
 
Nivolumab should be withheld and corticosteroids initiated at
 
	permanently discontinued.  If improves:  Continue steroids until grade 1, then taper over at least 1 month.  Upon improvement, nivolumab may be resumed after corticosteroid taper. If worsening or no improvement occurs despite initiation of corticosteroids, nivolumab must be permanently discontinued.

	a dose of 1-2 mg/kg/day methylprednisolone equivalents.	If persists > 3-5 days or recurs  after improvement:  • Consider adding Infliximab 5  mg/kg (if no contraindication).  Note: Infliximab should not be used in cases of perforation or sepsis.

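### For drug-related Grade 3 diarrhoea or colitis, Protocol Sections 6.6 and 6.2 stop nivolumab, but the Grade 3 row of 6.6.1 allows it to resume after a steroid taper

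*Protocol*

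**What the plan says.** Three places in the Protocol set the action for drug-related Grade 3 diarrhoea or colitis.

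- **Section 6.6** (dose table). Grade 3 goes off protocol therapy, as does Grade 4. For Grade 2 the site may observe and treat symptoms for a week: "If persists greater than seven (7) days, then off protocol therapy". Below the table, for any grade: "Patients who require steroids should be taken off study treatment". The section then sends the reader to 6.6.1 for management.
- **Section 6.2** (general rule). It opens with "Patients who have any Grade 3 or Grade 4 non-hematological toxicity" attributable to the drug and removes them unless the event is on a list of exclusions. Neither diarrhoea nor colitis is on that list. A second list of removals includes "Grade 2 non-hematological toxicity requiring systemic immunosuppressive therapy", with bowel named, and a bullet for Grade 3 colitis or diarrhoea lasting more than seven days. The section closes with two sentences. The first removes any non-haematological toxicity that delays therapy by more than seven days. The second says that other attributable toxicities are adjusted as in 6.3 to 6.12.
- **Section 6.6.1** (recommended algorithm). The Grade 3 row says to hold therapy and give methylprednisolone at 1-2 mg/kg/day, then "Continue steroids until grade 1, then taper over at least 1 month", then "Upon improvement, nivolumab may be resumed after corticosteroid taper". In that row, permanent discontinuation applies only if the patient worsens or fails to improve on steroids. The Grade 4 row makes discontinuation mandatory.

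Section 5.3 sets an outer limit: a delay of more than six weeks ends protocol therapy.

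**The concern.** One event leads to two dispositions. A site that follows 6.6 or 6.2 stops the drug. A site that follows the Grade 3 row of 6.6.1 may rechallenge a child whose severe colitis improved on steroids. Section 1.6.3 lists colitis among the most common drug-related immune events in the adult phase I study, so the situation is foreseeable.

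A site has reason to treat the algorithms as dosing rules. The pulmonary (6.7.1) and neurological (6.9.1) algorithms give the same Grade 3-4 action as their dose tables. Elsewhere the protocol defers explicitly when it wants to: the pancreatic table in 6.5 points to the exceptions in 6.2, and the skin algorithm in 6.4.1 acts as per protocol. The Grade 3 resumption line in 6.6.1 has no such pointer.

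For the analysis, toxicity-related discontinuation belongs to the secondary safety and tolerability objective (Section 2.2). Its count would depend partly on which section a site read.

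**Working it through.** The plan gives no figure to reproduce. The check has two parts.

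**1. The rules for a drug-related Grade 3 event**

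| Place | Action on nivolumab |
|---|---|
| 6.6, Grade 3 row | Stop |
| 6.6, sentence on steroids | Stop if steroids are needed |
| 6.2, opening rule | Stop (not on the exclusion list) |
| 6.2, later bullet | Stop if longer than seven days; silent on shorter events |
| 6.2, delay rule | Stop if delay exceeds seven days |
| 6.6.1, Grade 3 row | Hold, steroids, taper, may resume |

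The last row is the only one that permits resumption. The seven-day bullet is redundant under the opening rule. Because it names these two events with a duration, it can be read as letting shorter Grade 3 events continue.

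**2. Can resumption under 6.6.1 meet the delay limits?**

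Inputs:
- doses every 14 days, plus or minus 2 (5.2);
- taper *T* of at least one month, taken as 28 to 31 days (6.6.1);
- limits of 7 days (6.2) and 6 weeks, i.e. 42 days (5.3).

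Let *t* be the days from onset to Grade 1 and *s* the days from onset to the next due dose. Then delay past the due dose = *t* + *T* − *s*.

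- Shortest case: steroids start just after a dose, Grade 1 is immediate (*t* = 0) and *T* = 28. From the end of the dosing window (*s* = 16): 28 − 16 = **12 days**. From the nominal date (*s* = 14): 28 − 14 = **14 days**. These exceed the seven-day limit by 12 − 7 = 5 and 14 − 7 = 7 days.
- Onset on a due dose (*s* = 0, *t* = 0): **28 to 31 days**.
- Six-week limit with onset on a due dose: *t* + *T* ≤ 42 gives *t* ≤ 42 − 31 = 11 to 42 − 28 = 14 days. If Grade 1 takes longer than about 11 to 14 days, resumption breaks 5.3 as well.

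So resumption under the 6.6.1 Grade 3 row always breaks the seven-day limit and sometimes the six-week one.

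**Scale.** The protocol gives no rate for Grade 3 diarrhoea or colitis. Its adult figure for any Grade 3-4 treatment-related event is 14% (1.6.3), or 0.14 × 50 = 7.0 patients across all organs. If the rate for this event were 1%, 2% or 5% (assumptions, not limits), the expected number among 50 patients would be 0.5, 1.0 or 2.5. Divergent handling further requires improvement on steroids and a choice to rechallenge.

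**The case against.** The strongest reply is that the protocol does imply an order. The closing sentence of 6.2 sends only the *other* toxicities to 6.3-6.12, so 6.2 removals come first, and 6.2 already removes attributable Grade 3 diarrhoea and colitis. The 6.6.1 text is a permissive line in a table headed as recommended. In addition, Section 6 requires that the Study Chair or Co-Chair be notified of dose modifications, and a calendar footnote in 8.2 requires that delays be discussed.

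Much of this stands. A reader might infer that the protocol leaves the question wholly open; it does not, and the better reading is to stop. But the order is only implied, the 6.6.1 row does not invoke it, and the seven-day bullet in 6.2 blurs it. Consultation lowers the risk of divergence without removing the contrary instruction.

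A second reply is that the seven-day limit cannot be strict, since 6.7 lets Grade 2 pneumonitis resume after steroids. That weakens the delay argument as independent support. It does not touch the conflict between 6.6 and 6.6.1, which exists without any delay limit.

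Two wider readings are tempting and not supported:

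- *That Grade 2 is also a contradiction.* The Grade 2 row says "Nivolumab should be withheld per protocol" and, after steroids, "Resume nivolumab per protocol". Both defer to the protocol, under which a Grade 2 patient needing steroids is removed. The resumption line then has no use, but it gives no contrary order.
- *That 7.14 and 6.10 also authorise rechallenge after colitis.* Section 7.14 is headed as covering other immune-mediated events, and gastrointestinal toxicity has its own Section 7.7. Section 6.10 concerns treatment while progression is unconfirmed.

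**Conclusion.** The contradiction holds for drug-related Grade 3 diarrhoea and colitis: 6.6 and the opening rule of 6.2 stop nivolumab, and the Grade 3 row of 6.6.1 permits resumption. The delay result assumes that a month is 28 to 31 days and that resumption waits for the taper to finish, as the row says.

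This should be fixed. It is a safety instruction that conflicts with the protocol's own removal rule, and it can make recording of toxicity-related discontinuation inconsistent. A reader might infer that the response results are compromised or that the fault must be cured before anything else proceeds. The documents do not support that: no effect on the primary endpoint is shown, the numbers are probably small, and the implied order in 6.2 already favours stopping.

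**What to change.** 1. In the Grade 3 row of 6.6.1, replace the hold, withhold and resumption wording with: permanently discontinue nivolumab (see 6.2, 6.6). Keep the steroid and taper guidance.
2. In 6.2, delete the more-than-seven-day qualifier for Grade 3 colitis and diarrhoea.
3. Optional tidying: in the Grade 2 row of 6.6.1, replace the post-steroid resumption line with a reference to the removal rule in 6.2 and 6.6.

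Sections 7.14 and 6.10 need no change.

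The cost is amendment wording and a site memo. A few patients who might have been rechallenged under 6.6.1 will stop nivolumab. If the clinical team does not accept that loss, the alternative is to amend 6.2 (including its seven-day delay limit) and 6.6 to allow rechallenge on stated conditions, so that all three places agree.

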# **6.6.1** Recommended GI Adverse Event Management Algorithm

Opiates/narcotics may mask symptoms of perforation. Infliximab should not be used in cases of perforation or sepsis.

Toxicity (CTCAE	Management	Follow-up
v.4.03)  Grade 1  Diarrhea: < 4 stools/ day over baseline.  Colitis: asymptomatic.	

Continue protocol therapy

Symptomatic treatment

	
 
Close monitoring for worsening symptoms.
 
Educate patient to report worsening immediately.
 
If worsens:
 
Treat as Grade 2 or 3/4
 

Grade 2 Diarrhea: 4-6 stools/ day over baseline; IV fluids indicated <24hrs; not interfering with ADL. Colitis: abdominal pain; blood in stool.	
 
Nivolumab should be withheld per protocol.
 
Symptomatic treatment
 
	
 
Resume protocol therapy
 
If persists > 5-7 days or recurs:
 
0.5-1.0mg/kg/day         methylprednisolone or oral         equivalent
 
When symptoms improve to         grade 1, taper steroids over at         least 1 month
 
Consider prophylactic         antibiotics for opportunistic         infections
 
Resume nivolumab per         protocol.
 
If worsens or persists > 3-5 days         with oral steroids:         
 
Treat as Grade 3 or 4 and

Grade 3 Diarrhea: ≥ 7 stools/ day over baseline; incontinence; IV fluid ≥ 24 hours; interfering with ADL Colitis: severe abdominal pain, medical intervention indicated, peritoneal signs	
 
Hold protocol therapy
 
Corticosteroids at dose of 1-2 mg/kg/day methylprednisolone IV or IV equivalent
 
Add prophylactic antibiotics for opportunistic infections
 
Consider lower endoscopy
 
Nivolumab should be withheld and corticosteroids initiated at
 
	permanently discontinued.  If improves:  Continue steroids until grade 1, then taper over at least 1 month.  Upon improvement, nivolumab may be resumed after corticosteroid taper. If worsening or no improvement occurs despite initiation of corticosteroids, nivolumab must be permanently discontinued.

	a dose of 1-2 mg/kg/day methylprednisolone equivalents.	If persists > 3-5 days or recurs  after improvement:  • Consider adding Infliximab 5  mg/kg (if no contraindication).  Note: Infliximab should not be used in cases of perforation or sepsis.
Grade 4 Diarrhea or Colitis: life-threatening, perforation.	Nivolumab must be permanently discontinued, and corticosteroids should be initiated at a dose of 1 to 2 mg/kg/day methylprednisolone equivalents	
 
If improves:         
 
Continue steroids until grade                 1, then taper over at least 1                 month
 
 
 
If persists > 3-5 days or recurs         
 
after improvement:
 
Consider adding Infliximab 5                 mg/kg (if no contraindication).                      Note: Infliximab should not be used in cases of perforation or sepsis.
 
 
 

Patients on IV steroids may be switched to an equivalent dose of oral corticosteroids (e.g. prednisone) at start of tapering or earlier, once sustained clinical improvement is observed. Lower bioavailability of oral corticosteroids should be considered when switching to the equivalent dose of oral corticosteroids.

### **6.7** Dose Modifications for Pneumonitis

Pneumonitis	Management/Next Dose of Nivolumab
Grade 1	• Asymptomatic patients with radiographic changes should be managed with dose delay and consultation with respirology and infectious disease (ID). Nivolumab can be resumed at the same dose after the resolution of the radiographic changes.
Grade 2	
 
Hold dose until symptoms resolve, radiographic abnormalities improve to baseline and management with corticosteroids is completed. Resume no change in dose after pulmonary and/or ID consultation if lymphocytic pneumonitis is excluded.
 

Grade 3	Off protocol therapy

Grade 4 •	Off protocol therapy
-----------	----------------------

Distinguishing inflammatory pneumonitis is often a diagnosis of exclusion for patients who do not respond to antibiotics and have no causal organism identified including influenza. Most patients with respiratory failure or hypoxia will be treated with steroids. Bronchoscopy may be required and analysis of lavage fluid for lymphocytic predominance may be helpful. Patients with new lung nodules should be evaluated for sarcoid like granuloma. Please consider recommending seasonal influenza killed vaccine for all patients.

**Recommended management:** See Pulmonary Adverse Event Management Algorithm below (see *Section 6.7.1*).

## 6.7.1 Recommended Pulmonary Adverse Event Management Algorithm

Evaluate with imaging and pulmonary consultation. Rule out non-inflammatory causes. If non-inflammatory cause, treat accordingly and continue nivolumab therapy. Evaluate with imaging and pulmonary consultation.

Toxicity	Management	Follow-up
(CTCAE		
v.4.03)		
Grade 1	• Consider delay of protocol therapy	• Re-image with CXR every 3
Pneumonitis:	• Monitor for symptoms every 2-3	weeks
Radiographic	days	If worsens:
changes only.	• Consider Pulmonary and ID consults	• Treat as Grade 2 or 3-4
Grade 2	Hold infusion	• Re-image every 1-3 days
Pneumonitis:	Pulmonary and ID consults	If improves:
Mild to	• Monitor symptoms daily, consider	When symptoms return to near
moderate new	hospitalization	baseline, taper steroids over at
symptoms.	• 1 mg/kg/day methylprednisolone IV	least 1 month and then resume
	or oral equivalent	nivolumab therapy per protocol;
	• Consider bronchoscopy, lung biopsy	Consider prophylactic
		antibiotics.
		If not improving after 2 weeks
		or worsening:
		• Treat as Grade 3 or 4
Grade 3 or 4	Discontinue protocol therapy;	If improves to baseline:
Pneumonitis:	Hospitalize;	• Taper steroids over at least 6
Severe new	Pulmonary and ID consults;	weeks.
symptoms; new/		

worsening	• 2-4 mg/kg/day methylprednisolone	If not improving after 48 hours
hypoxia; life-	IV or IV equivalent;	or worsening:
threatening.	Add prophylactic antibiotics for	Add additional
	opportunistic infections;	immunosuppression (e.g.
	Consider bronchoscopy, lung	infliximab, cyclophosphamide,
	biopsy.	IVIG, or mycophenolate mofetil).

Patients on IV steroids may be switched to an equivalent dose of oral corticosteroids (e.g. prednisone) at start of tapering or earlier, once sustained clinical improvement is observed. Lower bioavailability of oral corticosteroids should be considered when switching to the equivalent dose of oral corticosteroids.

## **6.8** Dose Modifications for Fatigue

Fatigue	Management/Next Dose of Nivolumab					
Grade 1	No change in dose.					
Grade 2	No change in dose					
Grade 3	• Hold until ≤ Grade 2. If resolves within 7 days, resume at same dose level					

Fatigue is the most common adverse event associated with immune checkpoint therapy. Grade 2 or greater fatigue should be evaluated for associated or underlying organ involvement including pituitary, thyroid, and hepatic, or muscle (CPK) inflammation.

## **6.9** Dose Modifications for Neurologic Adverse Events

Neurologic events	Management/Next Dose of Nivolumab					
≤ Grade 1	Continue protocol therapy.*					
Grade 2	Hold until resolution to baseline.* Resume with no change in dose.*					
Grade 3	Off protocol therapy.					
Grade 4	Off protocol therapy.					

\*Patients with any CNS events including aseptic meningitis, encephalitis, symptomatic hypophysitis, or myopathy, peripheral demyelinating neuropathy, cranial neuropathy (other than peripheral n. VII), GB syndrome, myasthenia gravis should be taken off protocol therapy.

**Recommended management:** See Neurologic Adverse Event Management Algorithm below (see *Section 6.9.1*).

## 6.9.1 Recommended Neurologic Adverse Event Management Algorithm

Toxicity (CTCAE	Management	Follow-up			
v.4.03)					
Grade 1	Continue protocol	• Continue to monitor the patient.			
Neurological Toxicity:	therapy	If worsens:			
Asymptomatic or mild		• Treat as Grade 2 or 3-4.			
symptoms; Intervention					
not indicated.					
Grade 2	Delay infusion per	If improves to baseline:			
Neurological Toxicity:	protocol;	Within 7 days resume protocol			
Moderate symptoms;	• Treat symptoms per local	therapy, if persists >7 days			
limiting instrumental	guidelines;	discontinue protocol therapy.			
ADL.	• Consider 0.5 to 1.0	If worsens:			
	mg/kg/day	• Treat as Grade 3-4.			
	methylprednisolone IV or				
	oral equivalent.				
Grade 3-4	Discontinue protocol	If improves to Grade 2:			
Neurological Toxicity:	therapy;	• Taper steroids over at least 1 month.			
Severe symptoms;	Obtain neurology	If worsens or atypical presentation:			
limiting self-care ADL;	consult;	Consider IVIG or other			
life threatening.	• Treat symptoms per local	immunosuppressive therapies per			
	guidelines	local guidelines.			
	• 1-2 mg/kg/day				
	methylprednisolone IV or				
	IV equivalent;				
	Add prophylactic				
	antibiotics for				
D :: IV : I	opportunistic infections.				

Patients on IV steroids may be switched to an equivalent dose of oral corticosteroids (e.g. prednisone) at start of tapering or earlier, once sustained clinical improvement is observed. Lower bioavailability of oral corticosteroids should be considered when switching to the equivalent dose of oral corticosteroids.

